#### **4.2.6 General imputation rule for incomplete dates**

Where necessary for the calculation of derived variables, partial dates will be completed using the earliest calendar date based on the partial date provided. This rule is valid for all partial dates with the exception of the following:

- Start and stop dates of AEs

- Start and stop dates of concomitant medication
- Start and stop dates of study medication
- Start and stop dates of seizure diary data

Completely missing dates will not be replaced and the corresponding derived variables will be set to missing.

### **4.3 Interim analyses and data monitoring**

No informal interim analysis for determination of efficacy is planned for this study. To ensure subject safety, interim reviews of the safety data will be performed using an Independent Data monitoring Committee (IDMC). Serious adverse events and other significant events (detailed in Appendix 12 (section 12.2)) are monitored and will be triaged by the medical monitor and UCB Drug Safety in real time. After this triage, events will be passed on to the IDMC as appropriate. In addition, 3 interim reviews of safety data by the IDMC are planned when 25%, 50%, and 75% of subjects have been randomized and at study completion. Study enrollment will not be halted during planned IDMC review of the safety data. The objective, procedures, and timing of the IDMC safety assessments to evaluate risk and benefit for subjects in SP0969 will be described in the IDMC Charter.

A blinded sample size re-estimation will be performed when 50% of subjects have been randomized, completed the study (including those who discontinued), and have Baseline and post-Baseline seizure data available for analysis. See section 2.4.1 for details.

### **4.4 Multicenter studies**

This is a multicenter study. It is planned to appropriately pool centers by geographic location. The final strategy for pooling will be determined at the final DEM prior to unblinding the study.

Treatment by center interactions will be explored in the analysis.

### **4.5 Multiple comparisons/multiplicity**

There will be no adjustment for multiplicity in this study.

### **4.6 Use of an efficacy subset of subjects**

The primary efficacy variable will also be analyzed for the PPS. This analysis set will provide additional information on the analysis of the primary efficacy variable and the impact of the important protocol deviations on efficacy.

Other than the planned analyses based on the PPS, no other efficacy subsets are defined for statistical analyses.

### **4.7 Active-control studies intended to show equivalence**

This section is not applicable for this study.

### **4.8 Examination of subgroups**

Age at enrollment will be categorized into the subgroups:  $\geq 4$  to  $< 12$  years, and  $\geq 12$  to  $< 17$  years and used within summaries of disposition, demography, exposure, adverse events and certain efficacy analyses. Weight at Baseline will be categorized into the subgroups:  $< 30$ kg,  $\geq 30$ kg to

<50kg, and  $\geq$ 50kg, and used within summaries of exposure and adverse events. Further detail of these summaries is provided within the relevant subsections of sections 8 and 10.

Separate age subgroupings are used for the purpose of PedsQL summaries, and are detailed in section 8.3.3.

## **5 STUDY POPULATION CHARACTERISTICS**

### **5.1 Subject disposition**

The number of subjects screened, and the number and percentage of those subjects who were screen failures, broken down by primary reason for screening failure will be presented overall and repeated by age group, using the levels defined in section 4.8.

An overall summary of disposition for the SS will present the number and percentage of subjects randomized in the study, subjects completing the study, and subjects discontinuing along with the reason for discontinuation by treatment group and overall. This will be repeated for subjects in the FAS and also repeated by treatment group and age group for the SS.

In addition, an overall summary of disposition for the SS, as described above, will be broken down by study period (Titration, Maintenance, Transition and Taper Periods), treatment group and overall.

The date of first subject in, date of last subject out, number of enrolled subjects, and the number of subjects randomized, number of subjects in each treatment group, and overall, and the number of subjects in each analysis set (SS, FAS, PPS and PK-PPS), will be summarized overall and by investigator site. Subjects who transferred sites will be summarized according to their original site.

A summary of discontinuations due to AEs for all screened subjects will present the number and percentage of subjects who discontinued this study due to AEs broken down by type of AE.

The number and percentage of subjects enrolled under each protocol amendment (estimated by date of informed consent) will be presented. This will also be presented in the subjects data listings.

### **5.2 Protocol deviations**

Important protocol deviations defined in the important protocol deviation document, and additionally identified at the DEMs before unblinding of the database will be listed. In addition, the number and percentage of subjects with at least 1 important protocol deviation will be summarized overall and by category of important protocol deviation for the SS. The number and percentage of subjects with no important protocol deviations will also be summarized for the SS.

## **6 DEMOGRAPHICS AND OTHER BASELINE CHARACTERISTICS**

### **6.1 Demographics and other Baseline characteristics**

For subjects who only have a year of birth reported based on region-specific regulations, age will be obtained from the Interactive Voice Response System (IVRS) used to randomize subjects. Otherwise, age will be calculated relative to the date of informed consent. Weight will be summarized from Visit 1.

Body mass index (BMI) will be calculated using the subject weight recorded at Visit 1 (at study entry) as:

$$\text{BMI} = \text{weight in kilograms} / (\text{height in meters})^2$$

Age, age category ( $\geq 4$  to  $< 12$ , and  $\geq 12$  to  $< 17$  years of age), EudraCT age category ( $\geq 24$  months to  $< 12$  years, and  $\geq 12$  to  $< 18$  years), gender, weight (kg), weight band ( $< 30$ ,  $\geq 30$  to  $< 50$ ,  $\geq 50$  kg), height (cm), BMI ( $\text{kg}/\text{m}^2$ ), racial group (American Indian/Alaskan Native, Asian, Black, Native Hawaiian or Other Pacific Islander, White, and Other/Mixed), ethnicity (Hispanic or Latino, and not Hispanic or Latino), and vagus nerve stimulation (VNS) use (Active VNS, No VNS, and VNS not active) will be summarized by treatment group and overall for the SS, and repeated by treatment group and age group, using the levels defined in section 4.8.

A listing of reproductive potential and birth control measures for female subjects will be provided. No summaries of these findings are planned.

## **6.2 Medical history and concomitant diseases**

### **6.2.1 Medical history**

The number and percentage of subjects with a medical history condition, including both resolved and ongoing conditions at the time of study entry, will be summarized overall and by MedDRA® primary system organ class (SOC) and preferred term (PT) by treatment group for the SS.

Subjects who had any procedures of surgeries prior to study entry will be listed.

### **6.2.2 Concomitant diseases and conditions**

The number and percentage of subjects with concomitant diseases and conditions (medical history conditions noted as ongoing at study entry) will be summarized by SOC and PT for subjects in each treatment group for the SS.

## **6.3 History of epilepsy**

### **6.3.1 History of seizure types**

The number and percentage of subjects experiencing each seizure type (partial-onset seizures, generalized seizures, and unclassified epileptic seizures) at any time prior to study entry will be summarized by treatment group for the SS based on the ILAE Seizure Classification History eCRF.

A subject will be classified as having a history of partial-onset seizures if the subject has a history of simple partial (IA), complex partial (IB), or partial evolving to secondarily generalized (IC) seizures. A subject will be classified as having a history of generalized seizures if the subject has a history of absence (IIA1), atypical absence (IIA2), myoclonic (IIB), clonic (IIC), tonic (IID), tonic-clonic (IIE), and atonic (IIF) seizures.

### **6.3.2 History of seizure characteristics**

History of epileptic seizures, including the number and percentage of subjects with a history of withdrawal seizures, number and percentage with a history of status epilepticus, and with quantitative summaries of epilepsy duration and age at diagnosis will be summarized by treatment group for the SS.

The date of first diagnosis collected in the eCRF only includes month and year; the 1st of the month will be imputed for calculating epilepsy duration. The age at first diagnosis will be imputed using the 1st of the month or the subject's date of birth, whichever is later, if only the month and year are known, or January 1 of the same year or the subject's date of birth, whichever is later, if only the year is known.

### **6.3.3 Historical seizure count**

The historical seizure count eCRF records the number of seizures per pre-selected ILAE seizure code experienced by the subject during the 8 weeks prior to Baseline. These data will be provided in a subject data listing.

## **6.4 Prior and concomitant medications**

A listing of all medications taken during the study will be presented.

Medications will be attributed to the study periods as defined in section 3.2.2 based on the start date of the medication.

### **6.4.1 Number of Lifetime AEDs**

The number of lifetime AEDs defined as AEDs taken and stopped >28 days prior to Visit 1 (ie, prior to entry into the Baseline Period), or AEDs with a missing start date and unknown stop date, will be summarized by treatment group and overall for the SS based on the following categorization: 0 AEDs, 1 to 3 AEDs, 4-6 AEDs, and  $\geq 7$  AEDs.

### **6.4.2 Number of AEDs taken prior to the Baseline Period**

The number of AEDs taken prior to the Baseline Period defined as AEDs with a start date prior to the date of informed consent, ie, prior to entry into the Baseline Period, excluding lifetime AEDs, will be summarized by treatment group and overall for the SS based on the following categorization: 1 AED, 2 AEDs, and 3 AEDs.

The number and percentage of subjects taking AEDs prior to the Baseline Period will be summarized by WHODD chemical subgroup (Level 4) and preferred drug name, and by treatment group and overall for the SS.

### **6.4.3 AEDs taken during the Baseline Period**

The number and percentage of subjects taking AEDs during the Baseline Period defined as AEDs with a start date on or after the date of informed consent and prior to the first dose of study medication, and AEDs with a start date prior to the date of informed consent and with a stop date on or after the start of the Baseline Period, will be summarized, separately, by WHODD chemical subgroup (Level 4) and preferred drug name, and by treatment group and overall for the SS.

### **6.4.4 Number of AEDs taken on day of first dose of study medication**

The number of AEDs taken on the day of first dose of study medication will be summarized by treatment group and overall for the SS based on the following categorization: 1 AED, 2 AEDs, and 3 AEDs.

#### 6.4.5 Concomitant AEDs

The number and percentage of subjects taking concomitant AEDs defined as AEDs taken concomitantly for at least one day in common with study medication will be summarized, separately, by WHODD chemical subgroup (Level 4) and preferred drug name, and by treatment group and overall for the SS.

Vagus nerve stimulation is allowed and will not be counted as a concomitant AED.

#### 6.4.6 Non-AEDs taken prior to the Baseline Period

The number and percentage of subjects taking non-AEDs prior to the Baseline Period defined as medications with a start date prior to the date of informed consent, ie, prior to entry into the Baseline Period, will be summarized by WHODD anatomical main group (Level 1) and therapeutic subgroup (Level 2), and by treatment group and overall for the SS.

#### 6.4.7 Non-AEDs taken during the Baseline Period

The number and percentage of subjects taking non-AEDs during the Baseline Period defined as medications with a start date on or after the date of informed consent and prior to the first dose of study medication, and medications with a start date prior to the date of informed consent and with a stop date on or after the start of the Baseline Period, will be summarized by WHODD anatomical main group (Level 1) and therapeutic subgroup (Level 2), and by treatment group and overall for the SS.

#### 6.4.8 Concomitant Non-AEDs

The number and percentage of subjects taking concomitant non-AEDs defined as medications taken concomitantly for at least one day in common with study medication will be summarized by WHODD anatomical main group (Level 1) and therapeutic subgroup (Level 2), and by treatment group and overall for the SS.

### 7 MEASUREMENTS OF TREATMENT COMPLIANCE

The total weight of used oral solution (mg) will be calculated as:

$$(\text{Sum of actual weight of used oral solution [g]} / 1.1\text{g/mL}) \times 10\text{mg/mL}$$

Note that the estimated weight of 1mL of oral solution is 1.1g, and the concentration is 10mg/mL.

Where:

$$\text{Actual weight of used oral solution (g)} = \text{Total weight of bottles (including adaptors and caps) at Dispensation} - \text{Total weight of bottles (including adaptors and caps) at Return}$$

The expected weight of used oral solution (mg) will be calculated as:

$$\text{Sum of daily oral solution (mg) for each day in the corresponding time period}$$

Where:

$$\text{Daily oral solution (mg)} = (\text{Morning dose [mg/kg]} + \text{Evening dose [mg/kg]}) \times \text{Baseline weight (kg)}$$

Total amount of tablets (mg) will be calculated as:

---

$(100 \times [\text{number of 100 mg tablets dispensed} - \text{number of 100 mg tablets returned}] + 50 \times [\text{number of 50 mg tablets dispensed} - \text{number of 50 mg tablets returned}])$

Expected amount of tablets (mg) will be calculated as:

Sum of daily tablets (mg) for each day in the corresponding time period

Where:

Daily tablets (mg) = Morning dose (mg) + Evening dose (mg)

### Compliance

Compliance during a time period will be calculated using data from the respective time period only as follows:

$100 \times (\text{Total weight of used oral solution [mg]} + \text{Total amount of tablets used [mg]}) / (\text{expected weight of used oral solution [mg]} + \text{expected amount of tablets [mg]})$

A subject's dosing compliance should be within 75-125% during each visit. Compliance to study medication dosing will be calculated for each visit, and will also be determined for the Titration Period, Maintenance Period, and the entire Treatment Period (Titration+Maintenance Periods).

Compliance will be summarized separately for the Titration Period, Maintenance Period, and entire Treatment Period for the SS. It will be presented using descriptive statistics and additionally using the categorization <75%, ≥75% to ≤125%, and >125%.

## **8 EFFICACY ANALYSES**

The primary and secondary efficacy variables will be measured using data obtained from the subject diary. Subjects or parents/caregivers will keep a diary to record the daily seizure activity from the beginning of the Baseline Period until the last visit, recording both seizure type, seizure frequency, and whether the seizures were a cluster.

Each seizure code in the clinical database will be mapped to exactly 1 of the ILAE seizure codes based on the 1981 ILAE classification (Seizure Count eCRF).

The assessment of efficacy is based on seizure frequency, and will be analyzed primarily for the FAS. All CIs presented will be 95% 2-sided CIs.

For subjects who prematurely discontinue from the study, last observation carried forward method as described in section 4.2 will be applied to obtain a seizure frequency estimate for the Maintenance Period.

All efficacy variables will be listed.

### **8.1 Statistical analysis of the primary efficacy variable**

#### **8.1.1 Derivations of primary efficacy variable**

The primary efficacy variable is the change in partial-onset seizure frequency per 28 days from Baseline to the Maintenance Period. Seizure frequency per 28 days will be based on the number of days for which seizure information was provided during the specified time interval.

Seizure frequency per 28 days will be calculated as  $([\text{number of seizures over the specified time interval}] \text{ divided by } [\text{number of days in the interval}])$  multiplied by 28.

The partial-onset seizure frequency per 28 days will be calculated for both the Baseline Period and for the Maintenance Period, and the change from Baseline calculated.

If a seizure cluster is reported, the highest recorded daily seizure frequency during the Treatment Period for the seizure type associated with the report of a seizure cluster will be used as the imputed seizure frequency for the day on which the cluster occurred.

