#### Baseline Period

On or after the date of Visit 1 (entry to study) and prior to the date of first dose of study medication.

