#### Treatment Period

On or after the date of first dose of study medication and prior to or on the end date of the Treatment Period (Visit 8) for subjects who complete the Treatment Period, or on or after the date of first dose of study medication and prior to or on the date of the ETV for subjects who discontinue during the Treatment Period. If a subject does not have a Visit 8/ETV, then either the date of the last scheduled or unscheduled visit during the Treatment Period or the date of last known dose of study medication during the Treatment Period, whichever is later, will define the end date of the Treatment Period.

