### 3.3 Definition of Baseline values

In general, Baseline values for efficacy and safety variables will be determined from the last non-missing scheduled or unscheduled assessment prior to the first dose of study medication, unless otherwise noted for a specific type of data.

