#### **4.2.5 Incomplete dates for seizure diary data**

Seizure frequency and seizure-free days will be calculated over non-missing diary days during each time interval; days for which seizure diary data were not obtained will not be considered in the calculation of seizure frequency or seizure-free days. If more than 10% of the diary entries are missing for a specific subject and time interval, then that subject will not be considered for the calculation of seizure frequency or seizure-free days during that time interval.

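### SAP 8.1.1 fills a seizure-cluster day from the Treatment Period maximum without limiting the rule to on-treatment clusters, so a Baseline cluster day takes a post-randomisation count

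*SAP*

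**What the plan says.** SAP section 8 has the diary kept from the start of Baseline, "recording both seizure type, seizure frequency, and whether the seizures were a cluster". Clusters can therefore be reported before first dose.

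SAP 8.1.1 then states: "The partial-onset seizure frequency per 28 days will be calculated for both the Baseline Period and for the Maintenance Period". One cluster rule follows, for the whole section: "If a seizure cluster is reported, the highest recorded daily seizure frequency during the Treatment Period for the seizure type associated with" the reported cluster "will be used as the imputed seizure frequency for the day on which the cluster occurred".

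SAP 3.2.2 separates the two periods at first dose. Baseline is "On or after the date of Visit 1 (entry to study) and prior to the date of first dose of study medication". The Treatment Period is "On or after the date of first dose of study medication and prior to or on the end date of the Treatment Period". No Baseline day can lie in the window that supplies the imputed value.

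The derived Baseline frequency is used twice: log-transformed, as the covariate in the primary ANCOVA (SAP 8.1.2), and as the denominator of percent reduction for responders (SAP 8.2.2). Protocol 13.3.1 defines seizure frequency per 28 days but has no cluster rule.

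**The concern.** In the SAP sentence, the Treatment Period qualifies where the highest count is found. It does not qualify which clusters are covered. That leaves two ways to program it, each with a fault.

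- **Literal.** Any cluster day is covered. A Baseline cluster day takes a count observed after randomisation, so a quantity that should be fixed before treatment can depend on treatment.
- **On-treatment only.** Maintenance cluster days are raised to the subject's maximum and Baseline cluster days are not. The two halves of the change score are then counted differently, percent reductions fall, and the responder difference shrinks.

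Two programmers could produce different covariates and different responder lists from the same diary. The rule also gives no value for a subject with no counted Treatment Period day of that seizure type.

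**Working it through.** **The plan's own figures (SAP 2.4).** Difference -0.249, SD 0.73, 80% power, two-sided 5%:

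- n per arm = 2 × (1.960 + 0.842)² × (0.73/0.249)² = 134.9, that is 135, as stated.
- 1 - exp(-0.249) = 22.0%, as stated.
- SE = 0.73 × √(2/135) = 0.089, so the 95% CI around 22% is about 7% to 35%.

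None of these depends on the cluster rule.

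**One subject (assumed counts).** Baseline: 20 non-cluster seizures plus 2 cluster days in 56 days. Maintenance: 14 seizures in 70 days, so 14/70 × 28 = 5.6 per 28 days.

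- Literal, Treatment Period maximum 2: Baseline = (20 + 4)/56 × 28 = 12.0; reduction = (12.0 - 5.6)/12.0 = 53.3%, a responder.
- On-treatment only, recorded count 1 kept: Baseline = (20 + 2)/56 × 28 = 11.0; reduction = (11.0 - 5.6)/11.0 = 49.1%, a non-responder.
- Literal, Treatment Period maximum 4: Baseline = (20 + 8)/56 × 28 = 14.0. The same Baseline diary gives a different covariate because of what happened on treatment.

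**Simulation 1.** From the SAP: 56 Baseline, 42 Titration and 70 Maintenance days, and ANCOVA on ln(X+1) with ln(Baseline+1). Assumed: gamma-Poisson daily counts (shape 0.6), Baseline median 11 per 28 days (log SD 1.0), placebo improvement 15%, rate ratio 0.74, subject response log SD 0.45, half the log effect in Titration, at least 2 Baseline seizures, cluster days drawn at random from seizure days, no dropout or centre effect; two pools of 30,000 per arm.

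Scenarios: (a) clusters in 30% of subjects, on 10% of their seizure days; (b) 30% of subjects, 30% of days; (c) all subjects, 10% of days; (d) all subjects, 30% of days. Entries are reduction over placebo (%) / responder difference (points).

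| | True counts | Literal | Own-period maximum | Baseline maximum in both periods |
|---|---|---|---|---|
| a | 23.3 / 16.2 | 22.9 / 15.8 | 23.6 / 16.0 | 22.9 / 15.6 |
| b | 23.3 / 16.2 | 22.5 / 15.3 | 24.1 / 15.8 | 22.4 / 15.1 |
| c | 23.3 / 16.2 | 22.1 / 15.2 | 24.5 / 15.6 | 22.1 / 14.4 |
| d | 23.3 / 16.2 | 20.3 / 13.9 | 26.0 / 15.0 | 20.4 / 12.7 |

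Under the literal rule, the LCM-minus-placebo gap in mean ln(Baseline+1), net of chance, was -0.011, -0.023, -0.033 and -0.075 in a to d. Baseline does become treatment-dependent.

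**Simulation 2**, coded separately, lightest to heaviest clustering, with a Baseline cluster day keeping its diary count (taken as correct). True counts: 22.7 / 16.2.

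- Literal: 22.3 to 19.8 / 15.8 to 13.6. Responder loss 16.2 - 15.8 = 0.4 to 16.2 - 13.6 = 2.6.
- On-treatment only: 22.8 to 25.1 / 15.4 to 10.8. Responder loss 16.2 - 15.4 = 0.8 to 16.2 - 10.8 = 5.4; reduction overstated by 0.1 to 2.4.
- Own-period maximum: 22.9 to 24.8 / 15.8 to 14.5.

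Across the two simulations the literal rule lowers the reduction by 0.4 to 3.0 points (22.7 - 22.3; 23.3 - 20.3).

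**Simulation 3**, a different model: 135 per arm, 10% to 40% of subjects with 2 to 8 cluster days per 28 days. Literal v on-treatment only: reduction 22.3 v 22.9, 22.5 v 23.8, 22.7 v 24.9, 22.3 v 25.0; responder difference 12.1 v 11.8, 12.3 v 11.7, 12.2 v 11.0, 12.4 v 10.0. Without clusters the readings are identical (22.0% reduction).

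**No drug effect.** Rejection was 4.7% to 5.3% across rules in trials of 135 per arm built on simulation 1, and 3.7% to 4.5% in simulation 3.

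**The case against.** **The sentence is unrestricted, so there is nothing to interpret.** The literal reading is indeed the plainer one, and restricting it means adding words. But then the fault is the rule itself, since it puts post-dose counts into Baseline. SAP 3.3 pulls the other way: "Baseline values for efficacy and safety variables will be determined from the last non-missing scheduled or unscheduled assessment prior to the first dose". It does not settle the matter. It is a general rule that allows stated exceptions, and it describes a last assessment, not an eight-week rate.

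**On-treatment only is not one reading.** This stands. A Baseline cluster day might keep its recorded count or take the Baseline maximum. With the Baseline maximum the responder loss is much smaller (15.8 to 14.5 against 16.2 in simulation 2), and in simulation 3 it lies within about 0.3 points of the literal rule. The larger loss belongs to versions that leave Baseline cluster days unraised.

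**The size is assumed.** This stands too. In scenario (a) the literal rule moves the reduction by 0.4 points, inside a CI of about 7% to 35%; scenario (d) is an upper extreme. Simulation 3 also put the literal rule slightly above its no-cluster benchmark (22.3% to 22.7% against 22.0%), so its distance from the truth depends on the model. The gap between readings is the steadier finding.

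A reader might infer three stronger things.

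- *An uncounted cluster day is a missing diary day, so subjects lose their Baseline under SAP 4.2.5* ("If more than 10% of the diary entries are missing for a specific subject and time interval"). Not supported. That section concerns days without diary data, 8.1.1 counts days with seizure information, and 8.2.9 treats a seizure code with unknown count separately from a missing diary day. A reported cluster is diary data.
- *The rule inflates false positives.* The null simulations do not show it.
- *The contaminated covariate itself drives the primary estimate.* Using the Baseline maximum in both periods, with a clean Baseline, gives almost the same reduction as the literal rule (22.9, 22.4, 22.1, 20.4 against 22.9, 22.5, 22.1, 20.3).

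**Conclusion.** The point holds, as a faulty rule that should be corrected before unblinding. Followed as written, it lets post-randomisation counts into the covariate and the responder denominator whenever a Baseline cluster is reported. Restricted to on-treatment clusters, it counts the two periods differently.

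For the literal rule the assumed scenarios give a pull towards the null of about 0.4 to 3 points on the primary reduction and about 0.4 to 2.6 on the responder difference. For the on-treatment-only reading with recorded counts kept, the responder difference falls by about 0.8 to 5.4 points. Confidence is high in the gap in the text and low in the size, which rests wholly on cluster rates the documents do not give.

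**What to change.** Before unblinding, replace the cluster sentence in SAP 8.1.1 with:

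> A cluster day in the Baseline Period takes the subject's highest recorded daily count for that seizure type in the Baseline Period. A cluster day in the Titration or Maintenance Period takes the subject's highest recorded daily count for that seizure type in the Treatment Period. No data from on or after first dose enter the Baseline frequency. If no counted day of that type exists in the period, one fallback, set on blinded data and identical in both arms, applies.

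This keeps Baseline free of post-dose data and gave the responder difference closest to the true value in simulation 1 (16.0 to 15.0 against 16.2). It is not unbiased on the primary estimate: there it erred in the drug's favour by 23.6 - 23.3 = 0.3 to 26.0 - 23.3 = 2.7 points. So add one sensitivity analysis that uses the same Baseline-derived value in both periods, which erred towards the null (22.9% to 20.4% against 23.3%). It should inform interpretation and not act as a second success criterion, since requiring both to succeed would change the trial's decision rule and cost power.

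Tabulate cluster days by arm and period, so that readers can see whether the issue is material.

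Cost: a few SAP sentences, one extra analysis and some programming. No new data are needed.
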